#### **11.4.3.2 Dose Selection Data**

The evaluation of SYNT001 based on total IgG levels and responses on the PDAI total activity score from baseline will be summarized using descriptive statistics. Descriptive statistics will include mean, SD, coefficient of variation (CV), median, minimum, and maximum. The determination of dose and dosing duration of SYNT001 that achieves (i) total IgG level nadir decrease by  $\geq 60\%$  and  $\leq 90\%$  from baseline and (ii) a PDAI total activity score of  $\geq 50\%$  reduction from baseline to allow further clinical development in subject with pemphigus (*vulgaris* or *foliaceus*).

#### **11.4.4 Analysis of Secondary Endpoints**

##### **11.4.4.1 Pharmacokinetic Data**

PK results for SYNT001 will be summarized by cohort and timepoint.

Study drug serum concentrations will be used to calculate the following PK parameters:  $t_{1/2}$ ,  $C_{max}$ ,  $T_{max}$ , and  $AUC_{0-24}$  and  $AUC_{0-\infty}$  in Cohort 1 and  $C_{max}$  for Cohorts 2, 3, and 4 (optional cohort). PK parameters will be determined using noncompartmental method(s). Descriptive statistics will be provided for the PK parameters including mean, SD, CV, median, minimum, and maximum.  $T_{max}$  will be reported as median and range. All descriptive statistics will be performed on untransformed PK parameters and after  $\log_{10}$  transformation of PK parameters.

For calculation of mean concentrations and generation of mean concentration-time profiles, all below the limit of quantification (BLQ) values will be set to zero except when an individual BLQ falls between 2 quantifiable values, in which case it will be omitted.

If there are values above the BLQ, but too sparse to allow full analysis, descriptive statistics will be performed on available values.

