-----------------------------------	---

	
after the first dose of study drug will be summarized. Results for variables that are not coded will be presented in the listings as below, within, or above the normal limits of the central laboratory. Vital sign measurements will be summarized by cohort at each scheduled time point using descriptive statistics. PD/PK results will be summarized by cohort. Descriptive statistics of PD/PK parameters for SYNT001 will include mean, standard deviation (SD), coefficient of variation (CV), median, minimum, and maximum
 
Immunogenicity results will be summarized by cohort and timepoint. Descriptive statistics will include mean, SD, median, minimum, and maximum.
 
PDAI results will be summarized by score (total activity score, total damage score), cohort, and timepoint. Descriptive statistics will include absolute change from baseline and percent change from baseline.

--	--

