### **11.3 Sample Size Justification**

Formal sample size calculations were not performed. The number of subjects was chosen based on feasibility and was considered sufficient to meet the study objectives.

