### **11.4 Statistical Analysis**

#### **11.4.1 Statistical Analysis Plan**

Detailed methodology for summary and statistical analyses of the data collected in this study will be documented in a statistical analysis plan (SAP). The SAP may modify the plans outlined in the protocol; however, any deviations from the previously approved statistical plan will be described and justified in a SAP amendment. Additional statistical analyses other than those described in this section may be performed if deemed appropriate and will be described in the SAP. The SAP including pharmacokinetic data analysis methodologies will be finalized prior to database lock.

All descriptive and inferential statistical analyses will be performed using Statistical Analysis System (SAS) version 9.4 or later. Missing data will not be imputed unless otherwise stated. All clinical data captured will be provided in data listings.

Methods of handling of missing data for different endpoints will be further specified in the SAP. In general, where individual data points are missing because of insufficient samples, dropouts, or other reasons, the data will be analyzed based on reduced denominators unless specified otherwise in the SAP.

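### The PK section computes a CV on log10-transformed parameters, which depends on the reporting unit and is not a measure of between-subject variability; the valid CV on untransformed values is still reported beside it.

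*Protocol*

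**What the plan says.** The protocol treats PK summaries in two places.

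Section 11.4.4.1 (Pharmacokinetic Data) gives the list: "Descriptive statistics will be provided for the PK parameters including mean, SD, CV, median, minimum, and maximum". It restricts Tmax, which "will be reported as median and range", and then adds the general rule: "All descriptive statistics will be performed on untransformed PK parameters and after" log10 transformation. The parameters covered are half-life, Cmax, Tmax and the two AUCs in Cohort 1, and Cmax in the later cohorts. Neither a geometric mean, nor a geometric CV, nor a back-transformation is mentioned.

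The statistical considerations in the synopsis give the same list without any transformation: "Descriptive statistics of PD/PK parameters for SYNT001 will include mean, standard deviation (SD), coefficient of variation (CV), median, minimum, and maximum".

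Two further statements bear on weight. Section 11.3 says "Formal sample size calculations were not performed". Section 11.4.1 says "The SAP may modify the plans outlined in the protocol" and assigns the PK analysis methods to the SAP, which is not at hand.

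**The concern.** The general rule covers every statistic in the list, and CV is in the list. A CV is meaningful only on a ratio scale, where a change of unit multiplies the mean and the SD by the same factor and the ratio stays put. On a log scale a change of unit adds a constant to the mean and leaves the SD alone, so the ratio of SD to mean is a by-product of the chosen unit.

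A programmer who follows the section literally would produce a log-scale column with an uninterpretable CV in it. Someone reading that column for Cmax or AUC could take a figure near 5% as the between-subject variability when the true value is several times larger. The log scale is also the natural place to summarise Cmax and AUC, so the column is likely to be read.

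**Working it through.** The protocol states no PK value and no PK variability, so there is no figure of its own to reproduce. The check shows what the rule yields under assumed inputs.

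**Inputs**
- Statistics and scales: Section 11.4.4.1, as set out above.
- Assumed, not in the protocol: a log-normal Cmax with geometric mean 200 ug/mL and a true between-subject CV of 20%, 30% or 50%.

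**Formulas**
- SD of natural logs: s = sqrt(ln(1 + CV²)).
- SD of log10 values: s10 = s / ln(10) = s / 2.3026.
- CV of the log10 values, read literally: s10 / mean(log10 X), where the mean equals log10 of the geometric mean.
- Multiplying the unit by k adds log10(k) to that mean and leaves s10 unchanged.

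**True CV 30%**
- s = sqrt(ln 1.09) = 0.2936, so s10 = 0.2936 / 2.3026 = 0.1275.
- ug/mL: log10(200) = 2.301, and 0.1275 / 2.301 = 5.5%.
- ng/mL: log10(200,000) = 5.301, and 0.1275 / 5.301 = 2.4%.
- mg/mL: log10(0.2) = -0.699, and 0.1275 / (-0.699) = -18.2%.

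**Over the assumed range**

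| True CV | s10 | ug/mL | ng/mL | mg/mL |
|---|---|---|---|---|
| 20% | 0.0860 | 3.7% | 1.6% | -12.3% |
| 30% | 0.1275 | 5.5% | 2.4% | -18.2% |
| 50% | 0.2052 | 8.9% | 3.9% | -29.4% |

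**The error has no fixed direction.** With a geometric mean of 1.333 units, log10(1.333) = 0.125 and a true CV of 30% comes out at 102%. With a geometric mean of exactly 1 unit the denominator is zero and the ratio is undefined.

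**Half-life shows the same through the time unit.** For eight invented half-lives of 0.5, 0.6, 0.7, 0.8, 0.9, 1.0, 1.2 and 1.4 days, the arithmetic CV is 34.3% in either unit. The CV of the log10 values is -202% in days and +11.5% in hours.

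**A log-scale statistic that works.** Geometric CV = sqrt(exp(s²) - 1), with s = s10 × 2.3026. It returns 20%, 30% and 50% for the three true CVs in any unit. For eight invented Cmax values (120, 150, 170, 190, 210, 240, 280 and 340 ug/mL), it is 34.8% in ug/mL, ng/mL and mg/mL alike. The arithmetic CV of the same values is 33.9%.

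**The case against.** The case for leaving the text alone has four parts.

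- *The valid CV is reported anyway.* The rule asks for both scales, and the synopsis asks for the untransformed one. This stands and sets the size of the point: between-subject variability is neither lost nor replaced.
- *The protocol never defines the CV after log transformation as SD over mean of the logs.* A geometric CV is another way to give a CV from log-scale data. That is so, but the section asks for the listed statistics on transformed parameters and names no geometric quantity, so SD over mean is the plain reading.
- *The method is left to the SAP.* The SAP may well correct this, and the absence of a back-transformation from the protocol is not by itself a fault. What stands is narrower: the protocol does fix a rule here, and the rule as worded yields an invalid number.
- *Nothing depends on it.* The dose-selection endpoint uses total IgG and PDAI (Sections 3.4 and 11.4.3.2). The stated basis for dose recommendations is safety, PD and clinical outcomes (Section 9.5.1). No sample size was calculated and no interim analysis is planned. This also stands.

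A reader might go further and infer that the trial will report PK variability several-fold too small and so mislead later dosing. The documents do not support that. The correct arithmetic CV appears in the same output, the direction of the log-scale error depends on the unit, and no stated decision rule uses a PK CV.

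**Conclusion.** The point holds as a wording error in one sentence. Followed as written, Section 11.4.4.1 yields a log10-scale CV that changes with the unit and can understate, overstate, be negative or be undefined. The algebra needs no assumption. The sizes do: 5.5%, 2.4% and -18% for a true 30% rest on a log-normal parameter with an assumed geometric mean of 200 ug/mL, and they illustrate the effect rather than predict this trial's results.

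The error is confined to the log-scale summary of a secondary descriptive endpoint. The arithmetic CV of the untransformed values remains valid, and no dose-selection criterion, stopping rule or sample size stated in the protocol is affected. The correction is worth making because it is easy, not because a conclusion is at risk.

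**What to change.** Reword the last two sentences of that paragraph in Section 11.4.4.1 so that:

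- arithmetic mean, SD and CV are given for untransformed values only;
- for Cmax, AUC and half-life, the log10-scale statistics are replaced by the geometric mean and the geometric CV% = 100 × sqrt(exp(s²) - 1), where s is the SD of the natural-log values (equal to the SD of the log10 values × 2.3026);
- the rule on transformed summaries is stated not to apply to Tmax, which stays as median and range, as the section already provides.

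The SAP should carry the same formula. The cost is a sentence or two and standard PK output, with no new data and no change to the design.

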Study drug, dosage, and administration	
Study drug: SYNT001
 
Dosage:
 
Cohort 1: 10 mg/kg, 5 weekly IV doses
 
Cohort 2: ≤30 mg/kg, 5 weekly IV doses
 
Cohort 3: ≤30 mg/kg, 14 weekly IV doses
 
Cohort 4 (optional cohort): ≤45 mg/kg, ≤14 weekly IV doses
 
Product presentation and preparation:
 
SYNT001 provided as a liquid at a nominal concentration of 50 mg/mL. SYNT001 is diluted in dextrose 5% in water (D5W) to prepare the solution for infusion.
 
Route of administration: IV in 250 mL over 1 hour ± 15 minutes

Control, dose, and route of administration	Not applicable																										
Duration of subject participation	
The duration of subject participation for each cohort is as follows:
 
  
 Cohorta	Screening	Treatment	Follow-up	Maximum Total	
 
 Days	Weeks	
   
 1	≤14 days	28 days	84 days	126 days	18 weeks	
 
 2	≤14 days	28 days	84 days	126 days	18 weeks	
 
 3	≤14 days	91 days	84 days	189 days	27 weeks	
  
 
a. Planned dose and duration of subject participation for Cohort 4 (optional cohort) will be determined following DEC data review. All available data will be considered.
	Cohort a	Screening	Treatment	Follow-up	Maximum Total		Days	Weeks	1	≤14 days	28 days	84 days	126 days	18 weeks	2	≤14 days	28 days	84 days	126 days	18 weeks	3	≤14 days	91 days	84 days	189 days	27 weeks
Cohort a	Screening					Treatment	Follow-up	Maximum Total																			
		Days	Weeks																								
1	≤14 days	28 days	84 days	126 days	18 weeks																						
2	≤14 days	28 days	84 days	126 days	18 weeks																						
3	≤14 days	91 days	84 days	189 days	27 weeks																						

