- h. **PK**: Starting on Days 0 and 28, serum samples will be collected just prior to the start of study drug infusion (pre-dose), and at 5 minutes and 2, 4, 6, 24, and 48 hours after the end-of-study drug infusion. Additional samples will be collected on Days 5 and 33. See [Section 7.5.4](#) for additional information.
- i. **Immunogenicity**: Samples will be collected pre-dose when collected on dosing days. Samples will be collected on Days 0, 14, 28, 56, 84 and 112. See [Section 7.5.6](#) for additional information.
- j. Prior to **study drug infusion**, SYNT001 drug product is to be diluted in dextrose 5% in water (D5W) to a total volume of 250 mL and administered intravenously over 1 hour using a 0.2-micron inline filter. See [Section 4](#) and [Section 7.8](#) for additional information.
- k. **Immunoglobulins (IgG, IgA, IgM) and IgG subtypes (IgG1-4)**: Collected for measurements of IgG, IgG subtypes (IgG1-4), IgA, IgM at every visit. On Days 0, 7, 14, 21, and 28, samples are collected prior to infusion of study drug. See [Section 7.5.5](#) for additional information.
- l. **Exploratory pharmacodynamic samples (C3 and AECA)**: Collected pre-dose when collected on dosing days. See [Section 7.5.5](#) for complete information.
- m. Buccal samples to be collected and stored; pending review of clinical and pharmacodynamics assessments.
- n. Immunophenotyping by flow cytometry for measurement of CD3+CD4+ T, CD3+CD8+ T, monocytes, NK cells and B cells.
- o. Photographs of active lesions taken prior to first dose on Day 0. Follow-up photographs will be taken at Days 33, 56, 84 and 112. Subjects who begin a steroid taper will have additional photographs taken at the clinic visit during which the decision to begin the taper is made.
- p. Visit Days 5, 12, and 19 may be conducted via at-home nurse in lieu of a subject visit to the study site.
- q. Subjects will return to the clinic on Days 84 and 112 for follow-up visits. Subjects whose total IgG is not within 30% of their Day 0 baseline value and not above 500 mg/dL at the Day 112 visit will be referred for further management.

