- will be collected immediately prior to the infusion; 15, 30, and 45 minutes after the start of the infusion; at completion of the infusion; and 30 minutes, 1 hour, and 2 hours following completion of the infusion.
- c. **Pulse oximetry:** On Days 0, 7, 14, 21, and 28, pulse oximetry to be measured immediately prior to the infusion; 15, 30, and 45 minutes after the start of the infusion; at completion of the infusion; and 30 minutes, 1 hour and 2 hours following completion of the infusion.
  - d. **Clinical safety labs:** hematology, clinical chemistry, and urinalysis (see [Section 7.5](#) for a complete list). Full clinical safety laboratory draws will be collected at screening and on all study visits.
  - e. **Pregnancy test:** To be performed at time of screening, prior to first dose of SYNT001 on Day 0, and on Days 56 and 112. Urine or serum test is acceptable; however, positive urine tests must be confirmed with serum testing.
  - f. Digital 12-lead **ECG** to be obtained in triplicate at least 1 to 2 minutes apart and after 5 minutes of rest in a supine position. See [Section 7.6](#) for additional information. On treatment days to be obtained 5 minutes after the completion of infusion.
  - g. **Serology:** Any subject whose baseline value for tetanus or VZV was above the detectable level at baseline and is not within 30% of the baseline value or is below the protective level by End of Treatment will be referred to their primary care physician for further management. See [Section 7.5.3](#) for additional information.
  - h. **PDAI** will be administered at screening. Subject eligibility requires a PDAI total activity score >4. Thereafter, assuming eligibility, the PDAI will be administered during Treatment Period and Follow-up Period. See [Section 7.7](#) for additional information.
  - i. **PK:** On Days 0 and 28, serum samples will be collected just prior to the start of study drug infusion (pre-dose), and at 5 minutes, 1 and 2 hours after the end of study drug infusion. See [Section 7.5.4](#) for additional information.
  - j. **Immunogenicity:** Samples will be collected pre-dose when collected on dosing days. Samples will be collected on Days 0, 14, 28, 56, and 112. See [Section 7.5.6](#) for additional information.

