- Vital sign** measurements (sitting blood pressure, heart rate, respiratory rate, and oral temperature) to be obtained after 5 minutes of seated rest. Any abnormal measurements are to be repeated after 5 minutes of rest. Vital sign measurements will be taken on all study visits. On Days 0, 7, 14, 21, 28, 35, 42, 49, 56, 63, 70, 77, 84,

- 
- and 91, vital sign measurements will be collected immediately prior to the infusion; 15, 30, and 45 minutes after the start of the infusion; at completion of the infusion; and 30 minutes, 1 hour, and 2 hours following completion of the infusion.
- c. **Pulse oximetry:** On Days 0, 7, 14, 21, 28, 35, 42, 49, 56, 63, 70, 77, 84, and 91, pulse oximetry to be measured immediately prior to the infusion; 15, 30, and 45 minutes after the start of the infusion; at completion of the infusion; and 30 minutes, 1 hour and 2 hours following completion of the infusion.
  - d. **Clinical safety labs:** hematology, clinical chemistry, and urinalysis (see [Section 7.5](#) for a complete list). Full clinical safety laboratory draws will be collected at screening and on all study visits.
  - e. **Pregnancy test:** To be performed at time of screening, prior to dosing of SYNT001 on Days 0, 42, and 91, and on Days 119 and 175. Urine or serum test is acceptable; however, positive urine tests must be confirmed with serum testing.
  - f. Digital 12-lead ECG to be obtained in triplicate at least 1 to 2 minutes apart and after 5 minutes of rest in a supine position. See [Section 7.6](#) for additional information. On treatment days to be obtained 5 minutes after the completion of infusion.
  - g. **Serology:** Any subject whose baseline value for tetanus or VZV was above the detectable level at baseline, and is not within 30% of the baseline value or is below the protective level by End of Treatment will be referred to their primary care physician for further management. See [Section 7.5.3](#) for additional information.
  - h. **PDAI** will be administered at screening. Subject eligibility requires a PDAI total activity score >4. Thereafter, assuming eligibility, the PDAI will be administered during Treatment Period and Follow-up Period. See [Section 7.7](#) for additional information.
  - i. **PK:** Starting on Days 0 and 91, serum samples will be collected just prior to the start of study drug infusion (pre-dose), and at 5 minutes, 1 hour and 2 hours after the end of study drug infusion. [Section 7.5.4](#) for additional information.

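### The rule for values below the limit of quantification (BLQ) is not limited to one dosing interval, so in Cohorts 2 and 3 any BLQ trough is dropped and the mean trough is overstated

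*Protocol*

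**What the plan says.** Section 11.4.4.1 of the protocol applies its BLQ rule "For calculation of mean concentrations and generation of mean concentration-time profiles": BLQ values are "set to zero except when an individual BLQ falls between 2 quantifiable values, in which case it will be omitted". It does not confine the rule to one dosing interval or one sampled profile, and it makes no separate provision for pre-dose samples. The same section states "PK results for SYNT001 will be summarized by cohort and timepoint", so the pre-dose mean on the last dosing day is a reported figure.

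Dosing is weekly, but PK is sampled only around the first and the last dose:

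- **Cohort 1** ("Cohort 1: 10 mg/kg, 5 weekly IV doses"), Table 2 footnote h: "Starting on Days 0 and 28, serum samples will be collected just prior to the start of study drug infusion (pre-dose"), then at 5 minutes and 2, 4, 6, 24 and 48 hours after the infusion. "Additional samples will be collected on Days 5 and 33"; Sections 8.2.3 and 8.2.12 place both at 120 hours after the end of infusion.
- **Cohort 2**, Table 3 footnote i: "On Days 0 and 28, serum samples will be collected just prior to the start of study drug infusion (pre-dose"), then at 5 minutes, 1 hour and 2 hours.
- **Cohort 3**, Table 4 footnote i: "Starting on Days 0 and 91, serum samples will be collected just prior to the start of study drug infusion (pre-dose"), then at 5 minutes, 1 hour and 2 hours.

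**The concern.** Omitting a BLQ between two measurable values makes sense inside a single dosing profile, where such a result is more likely an assay fault than a real absence of drug. Across doses the logic fails. A trough that has fallen below the limit, followed by a new infusion, is a genuine low value, yet it also lies between two measurable ones. Dropping it removes the subjects with the lowest exposure from the mean trough, so the error has a fixed direction. That mean cannot fall below the LLOQ, and it is undefined if every trough is BLQ. At stake is the accuracy of the reported trough concentration by cohort.

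**Working it through.** The protocol gives no figure to reproduce here, so the check applies the written rule to each sampling schedule and then sizes the effect.

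**Step 1. Which BLQ results are dropped.** Three readings are possible:

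- (a) The rule runs over the subject's whole series, which is the plain wording.
- (b) The word *individual* means one isolated BLQ whose two neighbouring samples are both quantifiable.
- (c) The rule runs separately within each sampled profile.

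All post-infusion samples up to 2 hours (Cohorts 2 and 3) or 48 hours (Cohort 1) are taken as quantifiable.

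| BLQ result | (a) whole series | (b) isolated BLQ | (c) per profile |
|---|---|---|---|
| Cohorts 2 and 3: last-dose pre-dose trough | omitted | omitted | zero |
| Cohort 1: Day 28 pre-dose BLQ, Day 5 quantifiable | omitted | omitted | zero |
| Cohort 1: Day 5 BLQ, Day 28 pre-dose quantifiable | omitted | omitted | zero |
| Cohort 1: Day 5 and Day 28 pre-dose both BLQ | both omitted | both zero | both zero |
| Cohort 1: Day 33 BLQ (last PK sample) | zero | zero | zero |

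In Cohorts 2 and 3 the trough's immediate neighbours are the 2-hour first-dose sample and the 5-minute last-dose sample. A BLQ trough is therefore dropped under both (a) and (b).

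**Step 2. Size for the mean trough.** Let k of n troughs be BLQ (0 < k < n), and let the quantifiable troughs have mean m, in units of the LLOQ.

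- Mean under the rule: m.
- Mean with BLQ set to zero: (n−k)m/n, so the ratio is n/(n−k).
- True mean: at least (n−k)m/n and below [(n−k)m + k]/n, because each BLQ value is between 0 and 1 LLOQ.

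The protocol gives no concentrations, so m = 5 is an assumption:

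| n | k | Rule | Zero-set | True mean | Overstatement |
|---|---|---|---|---|---|
| 4 | 1 | 5.0 | 3.75 | 3.75–4.0 | 1.25–1.33 |
| 4 | 2 | 5.0 | 2.5 | 2.5–3.0 | 1.67–2.0 |
| 4 | 3 | 5.0 | 1.25 | 1.25–2.0 | 2.5–4.0 |
| 8 | 2 | 5.0 | 3.75 | 3.75–4.0 | 1.25–1.33 |
| 8 | 4 | 5.0 | 2.5 | 2.5–3.0 | 1.67–2.0 |

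The lower end moves with m. For n = 4 and k = 2, m = 2 gives 2/[(2×2+2)/4] = 2/1.5 = 1.33, and m = 10 gives 10/[(2×10+2)/4] = 10/5.5 = 1.82. The upper end stays at 4/2 = 2.0.

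**Step 3. Cohort 1 at 120 hours, reading (a) only.** Take 8 subjects with identical results after doses 1 and 5 and an assumed quantifiable value of 2 units. With 2, 4 or 6 subjects BLQ, the Day 5 mean is 2.0 each time (BLQ omitted). The Day 33 mean is 6×2/8 = 1.5, 4×2/8 = 1.0 or 2×2/8 = 0.5 (BLQ set to zero). Identical data then show an apparent fall of 25%, 50% or 75%.

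**Step 4. When BLQ troughs would occur.** Neither LLOQ nor half-life is given. With mono-exponential decline from a peak R times the LLOQ, a sample at time t is BLQ if the half-life is below t/log2(R). For R = 100, 1,000 and 10,000 the 168-hour trough is BLQ below about 25, 17 and 13 hours, and the 120-hour sample below about 18, 12 and 9 hours.

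**The case against.** The strongest reply is that the rule concerns mean concentration-time profiles and PK is sampled as two separate profiles, so an analyst would naturally apply it within each. That reading removes the problem entirely, but the protocol does not state it. Section 11.4.1 leaves PK methodology to the SAP, which could supply the limit. The SAP is not at hand, however, and the rule as the protocol fixes it gives a biased mean when followed.

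A reader might infer more than the documents support:

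- **That every BLQ trough is lost in all cohorts, and that Day 5 versus Day 33 is bound to show a false fall.** In Cohort 1 this needs the whole-series reading. A subject BLQ at 120 hours would usually also be BLQ at the 168-hour Day 28 pre-dose sample. Those are adjacent PK samples, so if *individual* means one isolated BLQ, both become zero, as on Day 33. No comparison of Day 5 with Day 33 is planned either.
- **That PK parameters or dose decisions are distorted.** The BLQ rule is stated only for mean concentrations and profiles, not for Cmax, Tmax, AUC or half-life. No trough endpoint is defined (Sections 3.5 and 7.5.4). Dose recommendations are tied to safety and pharmacodynamic review (Table 5), and the dose-selection endpoint to IgG and PDAI (Section 3.4).
- **That subjects with anti-drug antibodies are selectively removed.** Section 7.5.6 mentions neutralization and possible loss of efficacy. It does not say that concentrations fall below quantification.

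Section 11.4.2 also reports the number of observations, and all clinical data are listed, so dropped values would show as a smaller n. That makes the loss visible but does not correct the mean.

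**Conclusion.** The point holds in a limited form, with low severity. In Cohorts 2 and 3 any BLQ trough is omitted under both the plain and the isolated-BLQ reading, and the mean trough is then biased upward. The ratio n/(n−k) is exact against zero-setting but only an upper bound against the truth, since zero-setting is itself biased low. In Cohort 1 the omission, and the unequal handling of a 120-hour BLQ on Day 5 and Day 33, depend on the reading chosen. The sizes above rest on assumed concentrations, and the document does not show whether any trough will be BLQ. What is affected is a set of descriptive secondary summaries.

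**What to change.** In Section 11.4.4.1, and in the SAP to match, limit the omission to a BLQ between two quantifiable values within the same dosing interval. State that a pre-dose BLQ, or a BLQ that is the last sample before the next dose, is set to zero like other BLQ values. Report the number BLQ at each timepoint beside the mean. A BLQ trough then stays in the mean as zero in every cohort, and a 120-hour BLQ in Cohort 1 is zero on both Day 5 and Day 33.

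The cost is one sentence and one count per timepoint. The downside is that mean troughs become lower where BLQ values occur, and somewhat below the true mean; the BLQ count lets the reader see how far that could matter.
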